- 1.2 Specific Aims: List the goals of the proposed study (e.g., describe the relevant hypotheses or the specific problems or issues that will be addressed by the study).1) Treat painful amputation sites in 30 patients with fat grafting to provide additional subcutaneous tissue padding over bony structures and nerve trunks. Limb anatomy and healing of the graft over time, along with stability/persistence of the new tissue, will be assessed by high resolution CT scanning with 3D reconstruction. Patients will be followed for 24 months after treatment to define long term outcomes. The primary outcome measures will be pain at the amputation site and improved ability to tolerate a prosthesis. Patients will be randomized to receive either standard fat grafting (15 patients) or cell enriched fat grafting (15 patients) utilizing the Tissue Genesis Cell Isolation System (CIS). Patients will be enrolled who have pain at an amputation site that limits function and/or interferes with the ability to use a prosthesis.2) Assess biologic properties of the cells within the fat graft and correlate with clinical outcomes. This will include adipose stem cell yield per volume of fat tissue, cell proliferation, capacity for adipogenic differentiation, lipolysis, and cell sub-population analysis by multiparameter flow cytometry. Results of these assays will be correlated with graft volume retention to search for predictors of good clinical outcome that are related to variation in adipose biology between subjects.3) Measure quality of life in patients before and after autologous fat grafting using validated psychosocial measures. This will include, among other tools, SF 36, the Beck inventory, and instruments designed for assessing limb function.

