Post-operative assessments for clinical outcomes of treatment include amputation stump form and pain assessment, evaluation by prosthetics and occupational therapy, nutritional evaluations (baseline, POV1 and POV3 only) and QOL measures will be performed at 7-21 days, 2, 3, 6, 12 months and at 24months after treatment. Patients will be followed for approximately 2 years after surgery; the structure of these visits is outlined below. There are no more follow-up procedures planned or anticipated after post-op visit 6. Post op study visit (Day 3-6): This study visit will occur with the study investigator or research team and will take place approximately in 3-6 days post surgical procedure for the purpose of incision assessment and potential suture removal, if applicable. The entire visit will take approximately 30-45 minutes and will be scheduled with the subject prior to hospital discharge post fat graft procedure. 1. Limited medical history and physical exam with a limb exam completed by the PI and /or the Co-investigator 2. Adverse Event Reporting (Should an adverse medical event occurred prior to the visit and be reported by the subject, the research team will do due diligence to collect information pertaining to the event through subject report and /or medical record review and /or referring physician report) 3. Collection of subject's medication profile to include prescription and vitamins / supplements, allergies, vital signs (Blood Pressure, Heart rate, respirations, temperature) and collection and distribution of Post-operative Diary Card and Pain Log . The subject will be asked to continue logs if an event/issue persists beyond normal post op healing, until the next post-op visit (POV1) POSV1-6 (Post-Operative Study Visits 1-6) The following study visits will occur with the study investigator or research team and will take place at 7-21 days (POV1), month 2 (POV2), month 3 (POV3), month 6 (POV4), month 12 (POV5) and two years (POV6) (+/- 2 weeks) after the surgical fat grafting procedure. The duration of time for each visit will be approximately 3-4 hours. All visits will be scheduled by the research coordinator and discussed with the subject prior to the fat graft procedure. The following research procedures will be completed at this visit: 1. Collection of subject's medication profile to include prescription and vitamins / supplements, allergies, vital signs (Temp, HR, Resp, BP) and weight and BMI calculation and post operative pain assessment 2. Limited medical history & physical exam including amputation stump completed by the PI and /or the Co-investigator. The investigator will rate the appearance/volume of the graft site using the limb volume and appearance grading scale 3. Adverse Event Reporting (Should an adverse medical event occurred prior to the visit and be reported by the subject, the

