
measure physical function and symptoms in people with musculoskeletal disorders of the upper limb. The DASH is estimated to take approximately 10 minutes or less.f. Functional Mobility Assessment (FMA) is a self-report questionnaire to assess perceived user function related to assistive technology use. The FMA is expected to take approximately 10 minutes or less.g. Prosthetic Device Use History: Compliance with prosthesis use affects activities of daily living (ADLs) as well as impacting social interaction. The participant's prosthetic devices (both pre and post procedure) will be evaluated and a history will be obtained from the participant to determine average daily use and related issues/concerns. This questionnaire is estimated to take approximately 30 minutes for the subject to complete.h. Physical Examination: A physical examination will be conducted to evaluate general UE and LE function and specifically the amputation stump. The stump characteristics will be recorded, including measurements, range of motion, strength, skin integrity/areas of pressure, pain and prosthesis/socket interface. This physical examination is anticipated to take approximately 30 minutes to complete. If upon examination, it is determined that the participant is at increased risk for developing pressure ulcers and/or the participant's current wheelchair and seating is not addressing their needs, they will be referred to the UPMC Center for Assistive Technology for a full assistive technology evaluation per routine clinical care.6. CT Scan with 3D renderings or MRI (Visit 4 PO, Visit 5 PO and Visit 6 PO).7. All participants who are women of child bearing potential will receive a urine pregnancy dip test. If the test result is positive the subject will not continue to the CT or MRI scan. (Visit 4 PO, Visit 5 PO and Visit 6 PO)8. Psychosocial assessment (Visit 1 PO, Visit 3 PO, Visit 4 PO, Visit 5 PO and Visit 6 PO)will be conducted satisfaction with surgical outcomes, quality of life and functional outcomes and improvement in self-esteem, psychiatric distress, and psychological coping.9. Structured Clinical Interview for DSM-IV (SCID) (Visit 4, 5, and 6 PO only) to evaluate any change in the presence/absence of psychiatric disorders and will be compared to PGSV1 SCID results. This SCID will take approximately 45-60 minutes of the subject's time to complete.10. 2D Photographs will be collected at each of the post op visits 11. Limb Pain Assessment will be collected at each of the post op visits . 12. Core Needle Biopsy of fat grafting site - POV3 and POV5 only -(this will only be done with subjects where it is determined by the PI that the biopsy will not interfere with the desired outcome of the fat grafting). In subjects where the biopsy is considered to be appropriate, core biopsies will be taken from the area treated with standard fat graft or treated with SVF concentrated fat graft. These samples will be histologically analyzed for differences in vascularity and other evidence of in vivo activity. The samples will be processed within the UPMC system. The research coordinator will provide telephone follow up 48 to 72 hours to the subject post biopsy. This contact is to obtain a subject self report assessment of signs and symptoms of an adverse event post biopsy (i.e., excessive bleeding, redness, extreme tenderness, and potential signs of infection) as a post procedure standard of care safety assessment. Procedures for Study post operative visits #1-12 usually occur on the same day; however, due to coordination of participant's schedules and travel distance the procedures may be performed on different days as long as the completion of the procedures do not exceed a length of 4 days total. In

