Pain and Serial computed tomography imaging will be performed and measured as parametric data sets before fat grafting and afterwards at various time points using a paired t-test model. Repeated measures analysis of variance will be used to evaluate change over time in all outcome measures. Using standard conventions of alpha=0.05 and beta=0.8, an enrollment of thirty patients may provide sufficient power to detect a Cohen's effect size of about 0.9 which is anticipated to be adequate for detecting clinically meaningful differences in the volume of soft tissue. A composite functional score will be constructed from the prosthetics and occupational therapy evaluations and compared between study groups. The details of this analysis, including which evaluations will be included in the score and relative weight, can be best determined as the study progresses and initial data sets are acquired. Additionally, each assessment score from the specific tests will also be considered individually for comparison.

[reviewer notes-]

Section 2 - Research Design and Methods

2.19

Will this research be conducted in (a) a foreign country and/or (b) at a site (e.g., Navajo Nation) where the cultural background of the subject population differs substantially from that of Pittsburgh and its surrounding communities?* No

Note that copies of training records, licenses, certificates should be maintained in the study regulatory binder and are subject to audit by the Research Conduct and Compliance Office (RCCO).

Section: Section 2 - Research Design and Methods

In addition, individuals planning to conduct human subject research outside the United States must complete an optional module on the CITI training website: International Studies. Click [here](#) to access the instruction sheet for accessing optional CITI modules.

- 2.19.1 Address the following for each of the foreign/culturally different sites where this research will be conducted:
- Name of site
 - Name of authorized individual (e.g., IRB Chair) from the local IRB or other human subject protections entity that is responsible for the review and approval of the project; upload approval letter with an English translation, if applicable
 - Name and qualifications of the site collaborator responsible for the conduct of the research (e.g., site PI)
 - The anticipated number of subjects that will be enrolled at that site
 - If Federally funded, provide the Federalwide Assurance number (FWA) assigned to the site *

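### Section 2.18 names repeated-measures ANOVA for every outcome without a sphericity correction or a missed-visit rule; in its classical form the time and group-by-time tests would be too liberal, mainly for pain and psychosocial scores

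*Combined protocol and SAP*

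**What the plan says.** Section 2.18 names two methods. Pain and CT are tested before grafting and "afterwards at various time points using a paired t-test model". Then, for everything: "Repeated measures analysis of variance will be used to evaluate change over time in all outcome measures". No covariance structure, sphericity correction, missing-data method or analysis set follows.

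Section 2.7 puts the post-operative visits at "7-21 days (POV1), month 2 (POV2), month 3 (POV3), month 6 (POV4), month 12 (POV5) and two years (POV6"). Outcomes use different subsets of them:

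- **Pain:** "Limb Pain Assessment will be collected at each of the post op visits" (2.7), plus the pre-graft assessment (2.6) and an assessment at screening (2.5.1).
- **Psychosocial scores:** pre-graft (2.6), then visits 1, 3, 4, 5 and 6 (2.7).
- **CT or MRI volume:** pre-graft (2.6), then 6, 12 and 24 months (2.7).
- **Prosthetic and functional scores:** screening (2.5.1), then 6, 12 and 24 months (2.7).

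The design is "standard fat grafting (15 patients) or cell enriched fat grafting (15 patients"), and section 2.17 says the primary outcomes will be compared between these two groups.

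**The concern.** The classical repeated-measures F test for time, and for group by time, is valid only under sphericity: the differences between any two occasions must all have the same variance. Equal variances with equal correlations are enough for this, though not strictly required. Pain is measured at gaps of about two weeks to twelve months, so nearby visits will probably correlate more strongly than distant ones. Sphericity then fails and the uncorrected test is too liberal.

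The classical computation also needs a value at every occasion. Follow-up lasts two years, and the protocol expects travel difficulties (2.7) and allows participation to end for missed visits (5.7). Data collected from an incomplete patient would go unused.

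Among the methods named in 2.18, the paired t-test compares before with after and cannot compare arms. That leaves repeated-measures ANOVA as the only named method able to test whether the arms diverge over time, and the group-by-time test is one of those affected.

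**Working it through.** **The plan's own figure.** Section 2.18 gives no figure for the repeated-measures analysis. Its only calculation is "Using standard conventions of alpha=0.05 and beta=0.8, an enrollment of thirty patients may provide sufficient power" "to detect a Cohen's effect size of about 0.9". Read as a two-group comparison at 15 per arm, with beta meaning power, power = Φ(d√(n/2) − z). Here 0.9 × √7.5 = 2.465.

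- One-sided: Φ(2.465 − 1.645) = Φ(0.820) = 79.4%, which reproduces the claim.
- Two-sided: Φ(2.465 − 1.960) = Φ(0.505) = 69.3%, which does not.

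That statement does not concern the time or group-by-time tests, so the present point neither rests on it nor changes it.

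**Step 1: size of the within-patient tests.** The inputs from the documents are 15 patients per arm and the visit times above: 0, 0.5, 2, 3, 6, 12 and 24 months for pain; the same without month 2 for psychosocial scores; and 0, 6, 12 and 24 months for CT and prosthetic scores. The correlation patterns are assumed. The uncorrected two-group repeated-measures ANOVA was simulated with no true effect, 15,000 runs per case, with Monte Carlo error of about 0.2-0.3 points. The table shows rejection rates (%) at nominal 5%, spanning the time and group-by-time tests.

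| Assumed correlation | Pain (7 occasions) | Psychosocial (6) | CT, prosthetic (4) |
|---|---|---|---|
| Equal, 0.5 | 5 | about 5 | about 5 |
| Patient effect + decay + noise | about 6 | 6.0 | 5.5 |
| Decay, 1-month r = 0.5 | 6.2-6.4 | 5.7-5.9 | 5.0-5.1 |
| Decay, 1-month r = 0.8 | 7.9-8.1 | 7.1-7.2 | 4.9-5.2 |
| First-order by visit, 0.7 | 8.0-8.3 | 7.6-7.9 | 6.1-6.7 |
| Decay, 12-month r = 0.2 | 8-9 | 7.8-8.0 | 5.5-5.7 |
| Decay, 12-month r = 0.5 | about 10 | 8.8-9.1 | 6.2-6.4 |
| Decay, 12-month r = 0.7 | 10-11 | 9.2-9.7 | 6.8-7.0 |
| Decay, 12-month r = 0.9 | 10.8-11.4 | 10.0-10.2 | 7.0-7.2 |

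The ranges of about 6-10%, 6-9% and 5-6.5% cover the decaying patterns up to a 12-month correlation of 0.5. Slower decay adds about one point. Adding screening as an eighth pain occasion gives up to 11.9%. With a Greenhouse-Geisser correction, the group-by-time test falls to about 3.5-5% throughout. The between-group main effect stays at 4.7-5.6% without any correction.

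*Analytic check.* Box's approximation puts the true level at P{F[ε(k−1), ε(k−1)(N−2)] > F₀.₉₅[k−1, (k−1)(N−2)]}, where k is the number of occasions and N = 30.

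- Pain, 12-month r = 0.5: ε = 0.43, and the critical value on 6 and 168 df is 2.15. With ε-reduced df of about 2.6 and 72, the level is 10.9%, close to the simulated 10%.
- CT, same decay: ε = 0.79, and the critical value on 3 and 84 df is 2.71. The level is 6.5%, against 6.2-6.4% simulated.

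**Step 2: complete rows.** Patients with every post-operative value = 30 × (1 − m)^v, where m is the assumed chance of missing a visit, independent across visits, and v is the number of visits. The documents give no rate.

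| m | v = 6 (pain) | v = 3 (CT, prosthetic) |
|---|---|---|
| 2% | 30 × 0.98⁶ = 26.6 | 30 × 0.98³ = 28.2 |
| 5% | 30 × 0.95⁶ = 22.1 | 30 × 0.95³ = 25.7 |
| 10% | 30 × 0.90⁶ = 15.9 | 30 × 0.90³ = 21.9 |

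**The case against.** The strongest reply is that 2.18 is under-specified rather than wrong. It is a short answer on an application form for a pilot, and the method's name does not exclude a corrected test or a mixed-model version. This is fair, and it is why every figure here is conditional on the classical form. It does not remove the point: if another version is intended, the plan should say so before the data are seen.

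Three stronger readings are tempting, and the documents do not support them.

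- **All p-values are inflated by a known amount.** No correlation is given, and under equal correlation the test is exact. CT volume and prosthetic scores bear on two of the three primary outcomes in 2.17. They have at most four occasions, so their inflation is slight.
- **One missed visit deletes the patient.** The plan never says this; it is a property of the classical computation. Section 5.7 commits to measuring outcomes wherever functional evaluation is possible. Two-week visit windows (2.7) and reimbursed travel (6.2.1) should also limit missed visits.
- **The comparison of arms loses its validity or a stated amount of power.** The between-group main effect holds its level. The paired t-tests use two occasions each, so sphericity does not arise. A comparison at month 24 alone does not need all six visits, so six-visit deletion does not set its power.

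It can also be said that a Greenhouse-Geisser correction alone would restore the level. It would, but it would not bring back incomplete patients.

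**Conclusion.** The point holds in conditional form. The plan fixes neither how unequal correlation is handled nor what happens to patients with missed visits. Under the classical uncorrected method, the inflation matters for pain and psychosocial scores and is minor for CT volume and prosthetic scores. Its size depends on how fast correlation decays, which is unknown here.

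The loss of patients is likewise conditional, on the complete-row method and on missed-visit rates that are assumed. It could be small (about 3 of 30 at 2% per visit over six visits) or nearly half (about 14 of 30 at 10%). The change is worth making because one modest revision deals with both problems, not because the trial's comparison of arms is shown to be invalid.

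**What to change.** In 2.18, for continuous outcomes, replace repeated-measures ANOVA with a linear mixed model for repeated measures:

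- Fixed effects for group, visit (as a factor) and group by visit.
- All available visits from every patient, so that no one is dropped for a missed visit.
- REML estimation with Kenward-Roger degrees of freedom.
- Unstructured covariance for outcomes with three or four occasions, which needs 3 × 4 / 2 = 6 or 4 × 5 / 2 = 10 parameters.
- A fallback named in advance for pain and psychosocial scores, such as spatial-power in actual time with a patient random effect. Unstructured would need 7 × 8 / 2 = 28 parameters for pain and 6 × 7 / 2 = 21 for psychosocial scores, which 30 patients may not support.

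The cost is a few sentences and standard software. No visit, procedure or patient number changes. The small downside is that the fallback covariance must be specified in advance. The model also relies on missing values being explained by the observed data, which the plan should state.

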
recordings. 3.) All participants who are women of child bearing potential will receive a urine pregnancy dip test. If the test result is positive the subject will not continue participation in this research study. 4.) Collection and review of new medications to include prescription and vitamins / supplements, allergies and vital signs (Temp, HR, Resp, BP), weight, body mass index (BMI) calculation, and adverse event reporting. 5.) Serial Computed Tomography Imaging or MRI scan will be performed. A high resolution Computed Tomography (CT) Scan of the amputation stump will be performed at Presbyterian Hospital and will take approximately 60 minutes. This scan will be pre-procedural and will serve as a baseline. All CT scans will be performed on a 64-slice scanner (LightSpeed, GE Healthcare), using slice thickness of 1.25 mm and pitch of 1.375. kVp, mA, and FOV will be optimized to the subject and body part to be imaged. Soft tissue and bone kernels will be employed. These images will be volumetrically reformatted into coronal and sagittal planes for confirmation of findings. Additionally, surface-rendered volumetric reformats will be created emphasizing both bony structures and soft tissues. In the event that a CT scan is contraindicated or declined by a study participant, MRI will be performed using a 1.5 T MRI scanner (Signa HDx, GE Healthcare). The MR imaging protocols will include coronal and axial planes using T1-weighted spin echo sequences as well as coronal, axial, and sagittal planes using T2-weighted fast spin echo with fat suppression and/or short tau inversion recovery (STIR) sequences. Again, FOV, TR/TE time, acquisition time and other parameters will be optimized to the subject and body part to be imaged. Intravenous contrast will not be administered for either CT or MR imaging. Images will be reviewed by radiology. Volume measurements of the implanted material will be made on all post-procedural CTs or MRIs. These volumetric measurements are expected to be precise to within 5% of the actual volume of material. Trends in volume of tissue will be analyzed over time across the multiple CT or MRI scans. Both linear and volumetric measurements will be used to quantify implanted material. Subjects must remove compression sleeves prior to CT scans. 6.) To further evaluate pre-surgical amputation stump pain, the study coordinator will provide a Pain Assessment form to the participant to complete. This form will document the nature/charter of the discomfort limiting function and or interferes with their ability to use a prosthetic device. The subject will be instructed to document the discomfort to include frequency, location, intensity (1 to 10 scale with 10 as most intense), type of pain (physiological or phantom). It will include self interventions related to pain and use of prosthetic devices. 7.) Psychosocial Assessment: One of the aims of the proposed study is to evaluate pre- and post-operative quality of life and symptoms of psychological distress. This aim will also consider psychosocial factors (pre- and post- surgery) that predict psychological well-being and quality of life outcomes following surgery. The aim is important for identification of psychosocial factors that may play a role in and be critical to enhancing quality of life outcomes from amputation stump surgery. Participants will be asked to complete a psychosocial battery that includes: a) self-report measures of satisfaction with physical appearance, anxiety and depressive symptoms, social functioning and social avoidance and distress and; b) questionnaires that assess significant predictors of quality of life

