2.15.3 Will biological specimens be stored without identifiers or linkage codes? *

[reviewer notes-]

Section 2 - Research Design and Methods

2.16 Will research participants be asked to provide information about their family members or acquaintances?

* No

2.16.1 Describe what information about the third party will be obtained from the participant:

2.16.2 If the information about the third party is of a private nature, can the identity of the third party be readily ascertained or associated with this information?

*

Describe the private information that will be collected and recorded about the third party:

[reviewer notes-]

Section 2 - Research Design and Methods

Section: Section 2 - Research Design and Methods

2.17

What are the main outcome variables that will be evaluated in this study?

Primary outcomes: Improvement of pain at the amputation site, improved ability to tolerate a prosthesis, and generation of a stable volume of adipose tissue at the amputation site (as measured by clinical assessment by rehabilitation sciences and prosthetics team, quality of life measures, and high resolution imaging). This will be compared between the standard fat grafting group (n=15) and the adipose cell enriched fat grafting group (n=15). Secondary outcomes: Local and systemic complications resulting from fat graft procedure (infection, fat necrosis, hematoma, seroma); basic assays of adipose cell behavior to elucidate the functional properties of adipose cells used for grafting, with correlation to outcomes.

2.18

Describe the statistical approaches that will be used to analyze the study data.

* Addressed below:

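### Section 2.18 ties its detectable effect of about 0.9 to no test, sidedness or time point, misstates beta, and covers an outcome that not every section lists as primary

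*Combined protocol and SAP*

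**What the plan says.** **Power.** The power statement in section 2.18 opens: "Using standard conventions of alpha=0.05 and beta=0.8, an enrollment of thirty patients may provide sufficient power to detect". The magnitude it goes on to name, on Cohen's scale, is an "effect size of about 0.9 which is anticipated to be adequate for detecting clinically meaningful differences in the volume of soft tissue". The statement names no test, no sidedness, no time point and no per-arm numbers.

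**Tests named in the same section.** Pain and imaging are to be measured "before fat grafting and afterwards at various time points using a paired t-test model". The section adds: "Repeated measures analysis of variance will be used to evaluate change over time in all outcome measures". Neither sentence is linked to the 0.9, and neither names a between-group test for pain or volume.

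**Comparison planned.** Section 2.17 lists as primary "Improvement of pain at the amputation site, improved ability to tolerate a prosthesis, and generation of a stable volume of adipose tissue" and says: "This will be compared between the standard fat grafting group (n=15) and the adipose cell enriched fat grafting group (n=15". Section 3.12 also expects treatments to be examined within randomisation blocks.

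**Imaging available.** Section 2.6 provides a pre-graft scan: "This scan will be pre-procedural and will serve as a baseline". Section 2.7 provides three follow-up scans: "CT Scan with 3D renderings or MRI (Visit 4 PO, Visit 5 PO and Visit 6 PO". These fall at 6, 12 and 24 months.

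**The concern.** Two things do not fit together.

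First, a reader who takes the usual two-sided 0.05 test on 15 versus 15 does not get 0.9. On that reading the chance of missing a true 0.9 SD difference is about one in three, where the sentence implies one in five. Because the analysis behind 0.9 is not identified, nobody can tell whether that reading is the right one. Beta as printed would mean 20% power.

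Second, the one power figure is about volume, but the protocol has more than one list of primary outcomes and volume is not on all of them. Section 2.3 describes the trial as non-blinded. If the primary outcome is left open, it can be chosen after results are seen. A null result on volume could also be given more weight than its power supports.

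**Working it through.** **Inputs.** Alpha 0.05 and d = 0.9 (2.18); 15 versus 15 (2.17, 1.2); one baseline and three follow-up scans (2.6, 2.7). Intended power is read as 0.80. All results assume complete follow-up of 15 per arm. The documents give no standard deviation, raw difference or correlation.

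**Step 1: beta.** Taken literally, beta = 0.8 is power 0.20. A two-sided t-test on 15 versus 15 would then have a detectable d of 0.42, which is not the stated figure. So it is a slip for power 0.80.

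**Step 2: reproduce about 0.9 (two groups, one time point, unadjusted).**
- Normal approximation: d = (z for alpha + z for power) × √(2/15), where √(2/15) = 0.365. One-sided: (1.645 + 0.842) × 0.365 = **0.91**. Two-sided: (1.960 + 0.842) × 0.365 = **1.02**.
- Exact t-test: 28 degrees of freedom, noncentrality d × √(15×15/30) = d × √7.5, which is 2.465 at d = 0.9.

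| Test, 15 vs 15 | Critical t | Power at d = 0.9 | d with 80% power |
|---|---|---|---|
| One-sided 0.05 | 1.701 | 77.6% | 0.93 |
| Two-sided 0.05 | 2.048 | 66.3% | 1.06 |

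The stated figure is reproduced one-sided and not two-sided.

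**Step 3: the paired t-test in 2.18.** Two-sided, 80% power: 0.78 with n = 15 and 0.53 with n = 30, in units of the SD of within-patient differences. Neither is 0.9, and a before-after test within patients does not compare the randomised groups.

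**Step 4: two-sided between-group analyses that use more scans.** The correlations below are assumptions. d stays in single-scan SD units, and the noncentrality is d × √(7.5/v).

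| Analysis | v | Assumed correlation | Power at d = 0.9 |
|---|---|---|---|
| Baseline-adjusted, one follow-up scan (27 df) | 1 − r² | r = 0.3 | 70% |
| | | r = 0.5 | 78% |
| | | r = 0.53 | 80% |
| | | r = 0.7 | 91% |
| Mean of three follow-up scans (28 df) | (1 + 2ρ)/3 | ρ = 0.5 | 83% |
| | | ρ = 0.58 | 80% |
| | | ρ = 0.7 | 76% |
| | | ρ = 0.9 | 69% |
| Both together (27 df) | (1 + 2ρ)/3 − r² | ρ = r, any value | about 95% or more |
| | | ρ = 0.7, r = 0.3 | about 80% |
| | | ρ = 0.9, r = 0.2 | 71% |

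Here r is the correlation with baseline and ρ is the correlation between follow-up scans. When ρ = r, v is largest at ρ = 1/3, where v = 5/9 − 1/9 = 4/9 = 0.444; this gives the lowest power on that row, about 95%.

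**Step 5: the primary outcomes side by side.**

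| Place | Pain | Prosthesis tolerance or wear | Volume or retention |
|---|---|---|---|
| CS2.1 abstract, Specific Aim 1 | yes | yes | no |
| CS2.1 abstract, Study Design | no | yes | yes |
| 1.2 Specific Aims | yes | yes | no |
| 2.17 Main outcome variables | yes | yes | yes |
| 3.12 (major endpoint) | yes | yes | no |

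The abstract disagrees with itself. The power figure covers only the last column.

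**The case against.** The strongest reply is that 0.9 may be correct. A one-sided 0.05 test gives 0.91 to 0.93, so the figure is reproducible, and a reader who infers an arithmetic error goes beyond the documents. That stands: what is missing is the statement of which test was used.

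A second reply is that the two-sided two-sample t-test at one time point is an outside benchmark. The sentence just before the power statement plans repeated-measures analysis for all outcomes, and baseline and repeated scans exist. That also stands in part. A reader might infer that the trial really has 66% power. The documents do not support this, because Step 4 shows a range from 69% to 95% or more, depending on the analysis and correlations. But 2.18 describes repeated measures for change over time, does not connect it to the 0.9, and gives no correlation, so the plan cannot claim the higher values either.

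Third, this is a pilot, the sentence says only that thirty patients may suffice, and 3.12 builds 30 from five blocks of six without using 0.9. A reader might infer that more patients are needed, since a two-sided t-test would take 21 per arm for 80% power at 0.9. That does not follow, because n was not derived from 0.9.

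Fourth, the device-exemption application and the grant application are listed as attachments but are not in the supplied text, and may hold the derivation. The point therefore covers the supplied text only. For pain, 3.12 does give a reason for having no power statement: no quantitative reports were known.

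Finally, 2.17 answers the question on main outcomes directly and includes volume. That helps the link to 2.18, but does not remove the conflict with the other sections.

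**Conclusion.** The point holds as a defect of reporting and consistency that should be fixed. Beta is wrong as printed. The detectable effect of about 0.9 is not tied to a test, sidedness or time point. For 15 versus 15 at a single time point without adjustment, it matches only an undeclared one-sided 0.05 test. On the conventional two-sided reading, power at 0.9 is about 66% and the 80% detectable effect is 1.06. These two numbers assume complete follow-up and belong to that reading alone; they are not the power of every analysis the plan might use. A baseline-adjusted or repeated-measures between-group test could reach or exceed 80%, under correlations the supplied text does not state.

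Independently of the power calculation, the primary outcomes conflict between sections, and the only powered outcome is absent from Aim 1 (abstract and 1.2) and from 3.12.

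**What to change.** Keep 30 patients, and:

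1. In 2.18, replace beta = 0.8 with power 0.80 (beta 0.20).
2. State the between-group test, its sidedness and the time point or points behind the power figure, and give the number that matches:
   - two-sided two-sample t-test: d = 1.06, with power about 66% at d = 0.9;
   - one-sided t-test, declared as such: d = 0.93;
   - baseline-adjusted or repeated-measures between-group analysis: the resulting figure together with the correlations assumed.
3. Describe the paired t-test as a within-group analysis only.
4. Before between-group data are seen, make the primary outcome, or stated co-primaries, identical in the CS2.1 abstract (Aim 1 and Study Design), 1.2, 2.17 and 3.12. The choice is the sponsor's.
5. Say which outcome the power figure covers, and that the others have none.

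The cost is wording: no extra patients and no design change. The stated detectable effect becomes less favourable unless a one-sided test or assumed correlations are declared.
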